### 5.2 Registration Process

**Pre-Screening:** To register a patient, the following documents should be completed and faxed or e-mailed to the Coordinating Center:

- Fax Cover Sheet
- Pre-Screening Registration Form
- Signed Patient Consent Form – Pre-Screening
- HIPAA Authorization Form
- Pre-Screening Eligibility Screening Checklist

Once eligibility is verified, to complete the registration process, the Coordinating Center will:

- Assign/confirm a pre-screening patient study number
- Register the patient on the study for pre-screening
- Fax or e-mail the patient study number to the participating site
- Call the research nurse or data manager at the participating site and verbally confirm registration (if needed)

**Primary Study:** To register a patient, the following documents should be completed and faxed or e-mailed to the Coordinating Center:

- Fax Cover Sheet
- Registration Form
- Signed Patient Consent Form
- HIPAA Authorization Form
- Eligibility Screening Checklist
- Copy of Required Screening Tests and Scans

Once eligibility is verified, to complete the registration process, the Coordinating Center will:

- Assign a patient study number
- Register the patient on the study
- Fax or e-mail the patient study number to the participating site
- Call the research nurse or data manager at the participating site and verbally confirm registration.

## 6. TREATMENT PLAN

### 6.1 Agent Administration

Treatment will be administered on an outpatient basis. Reported adverse events and potential risks are described in Section 8.1.

There is a possible risk of anaphylaxis and the vaccine should be administered in a setting where emergency treatment is available. Administration should be immediately discontinued and the appropriate therapy instituted per institutional guidelines if there is a serious allergic reaction. The patient must be observed in the clinic for at least 60 minutes after each vaccine. If an anaphylactic reaction is suspected, this must be discussed with the IND Sponsor before the subject is given another dose of vaccine.

### 6.2 Blinding and Randomization

This is a non-blinded, non-placebo controlled, randomized, prospective study. Eligible patients will be randomized in a 1:1 ratio to receive TA-CIN in either the arm or the thigh. Randomization will occur after registration and prior to the planned first dose of TA-CIN. All participants and providers will know the arm to which subjects are randomized.

A master list of randomization assignments will be generated and will be delivered to the Research Pharmacy at each participating site and to other key personnel, as identified. Upon successful registration of a subject, randomization will occur by the appropriate study staff.

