## 5. REGISTRATION PROCEDURES

### 5.1 General Guidelines

**Pre-Screening:** Patients eligible for HPV16 testing must be entered on study centrally at the Sidney Kimmel Comprehensive Cancer Center at the Johns Hopkins University. All sites should call the Lead Study Coordinator/designee at the Coordinating Center. The fax cover sheet, Pre-Screening Registration Form, and Pre-Screening Eligibility Worksheet will be supplied to each participating site.

**Primary Study:** Eligible patients will be entered on study centrally at the Sidney Kimmel Comprehensive Cancer Center at the Johns Hopkins University. All sites should call the Lead Study Coordinator/designee at the Coordinating Center to verify drug availability. The fax cover sheet, Registration Form, and Eligibility Worksheet will be supplied to each participating site. If a patient does not receive protocol therapy following registration, the patient's registration on the study may be canceled. The Study Coordinator should be notified of cancellations as soon as possible.

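### Section 6.2 circulates the whole randomisation list to the sites and to unnamed staff in an open-label trial, so staff who enrol patients are not barred from knowing upcoming assignments

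*Combined protocol and SAP*

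**What the plan says.** Section 6.2 sets a 1:1 allocation to arm or thigh and describes the trial plainly: "This is a non-blinded, non-placebo controlled, randomized, prospective study". On who knows the result: "All participants and providers will know the arm to which subjects are randomized".

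On the mechanics, the same section has a master list generated in advance, which "will be delivered to the Research Pharmacy at each participating site and to other key personnel, as identified". The assignment step is: "Upon successful registration of a subject, randomization will occur by the appropriate study staff". Randomisation comes after registration and before the first dose.

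Registration itself is central. Section 5.1 says of the primary study: "Eligible patients will be entered on study centrally". Under Section 5.2, once eligibility is verified, the Coordinating Center assigns a study number, registers the patient, sends the number to the site and confirms by telephone. Releasing the assignment is not one of those steps.

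**The concern.** Randomisation balances the two groups on stage, prior treatment and fitness only if those who decide whether and when to register a patient cannot foresee the next assignment. A list already at the site, with open-ended access, does not secure that.

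The arm-versus-thigh choice depends on this balance. Section 12.5 picks the better site from raw numbers of responders rather than by a formal test, and Section 1 combines those data with toxicity to choose the site for later trials. The investigators also have a stated expectation: Section 3.7.2 presents mouse data favouring the hind leg. Selective registration, even if well meant, could tilt a comparison this small.

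**Working it through.** **1. Who may hold the list.** Section 6.2 names the site Research Pharmacies and a second group defined by no role. The people who randomise are also not identified by role. No section bars anyone who screens, consents or registers from either group.

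**2. Is there a concealment step?** I looked for sealed envelopes, release of one assignment at a time, or a rule separating list holders from enrolling staff. Sections 5.1, 5.2, 6.2 and 11.1 contain none. Randomising after registration fixes the order of events; it does not conceal a list already distributed.

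**3. Does the pharmacy need the list in advance?** Sections 6.3 and 8.1 give both groups the same product, dose and volume; the groups differ by injection site, with only a small difference in the permitted needle gauges. Nothing in the preparation steps calls for knowing future assignments.

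**4. What is not stated.** The documents do not give the method of sequence generation, any blocking or stratification, or whether the list is split by site. If one sequence serves both sites, a site would need to know the other's accrual to identify the next slot. Past assignments, visible because the trial is open label, help prediction only if the sequence is restricted; the only restriction stated is the limit on group size in Section 12.2.

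**5. Size.**

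*The plan's own figures.* Section 12.2 takes 7 per group and thigh versus arm response rates of 65% v 45%, then 60% v 45%. With X_T and X_A independent binomials, P(X_T > X_A) = sum over i > j of b(i; 7, p_T) × b(j; 7, p_A).
- 65% v 45%: 69.3% (ties 15.8%), against a stated figure of about 70%.
- 60% v 45%: 62.1% (ties 17.9%), against a stated figure of about 60%.

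Both agree with the plan.

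*Step size.* One patient is 1/7 = 14.3 points of observed response rate. The expected effect of substituting one patient for another is the difference in their response probabilities divided by 7. On assumed differences of 20 and 50 points this is 0.20/7 = 2.9 points and 0.50/7 = 7.1 points.

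*Sensitivity, on my assumption.* Suppose the two sites are truly equal at 45%, and selective enrolment creates an imbalance d in expected response, so that the rates become 45% + d/2 for thigh and 45% − d/2 for arm.

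| d (points) | P(thigh has strictly more responders) |
|---|---|
| 0 | 39.5% |
| 5 | 47.0% |
| 10 | 54.6% |
| 15 | 62.2% |
| 20 | 69.3% |

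A 20-point imbalance would reproduce the full planned effect. The documents give no value for d and no reason to expect one that large; the table shows sensitivity and is not an estimate.

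**The case against.** The strongest reply is that the text does not put the list in the hands of enrolling staff. Section 6.2 names pharmacies, which have no recruitment role anywhere in the protocol, and the staff who randomise could belong to the Coordinating Center. That stands: a reader might infer that enrollers know the next assignment, but the documents only leave it possible.

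There are also real restraints. The Coordinating Center verifies eligibility before registration, and the criteria in Section 4 are narrow. Section 12.3 implies (50 + 120) × 0.5 × 0.15 = 12.75 eligible patients a year over two services, about one a month, so staff would seldom have two candidates to put in order. Deferral runs into the 8-week disease assessment and 12-month treatment limits in Section 4.1 and the 60-day pre-study window in Section 10. It would therefore be wrong to say that nothing stops steering, or that concealment is the comparison's only protection.

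These points reduce the opportunity; they do not close it. Eligibility checks keep out ineligible patients but do not prevent an eligible one from being deferred or not offered entry. Laboratory endpoints limit biased measurement, not biased enrolment. Section 5.1 also allows registration to be cancelled if therapy is not given, and Section 1 allows discretionary replacement of some withdrawals, both of which leave further room for selection.

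That this is a pilot without a formal test of site lowers the stakes. It does not make the procedure sound, since the site choice is meant to carry forward.

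**Conclusion.** The point holds as a weakness in a stated procedure: a list fixed in advance goes to the sites and to an undefined group, in an open-label trial with no concealment described. It permits foreknowledge by enrolling staff and does not demonstrate it.

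Three stronger readings are tempting and not supported. First, that the comparison is biased: nothing in the documents shows steering. Second, that the bias is worth 14 points: that is the granularity of 7 patients and would describe a steered patient only if a certain responder replaced a certain non-responder. Third, that favouring less pre-treated patients would raise a site's response: Section 12.2 expects prior chemotherapy or radiotherapy to prime the response, so on the plan's own premise the direction could reverse.

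The size is therefore unknown. The conclusion rests on the wording of Sections 5 and 6.2 alone; a written procedure outside these documents that restricts access would largely answer it. The change is worth making because it is nearly free and protects a decision taken on raw counts.

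**What to change.** **In Section 6.2,** delete distribution of the master list to the sites and to the undefined group. State that it is held by a statistician or other named person who has no part in screening, consenting or registering patients at any site. This must cover the recruiting service at the Coordinating Center's own institution: Sections 5.1 and 12.3 show that this institution both coordinates and recruits, so moving the list there is not enough by itself.

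**In the Primary Study steps of Section 5.2,** add that the Coordinating Center releases only that patient's assignment, with the study number, once eligibility is verified and registration is complete. The site pharmacy learns the injection site from that confirmation.

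**For patients already randomised,** report who had access to the list and whether any of them took part in enrolment.

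**Cost.** Two short text changes and one extra item in a confirmation that is already sent. Sample size, visits and assays are unchanged. The drawback is that assignment depends on the Coordinating Center being reachable, which registration already requires.

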### 6.3 Dose Levels

The dose of TA-CIN is fixed. The site of administration is as assigned by randomization (as above).

Treatment Groups/Cohorts					
Group	TA-CIN Route of Administration	Volume (mL)	Dose (µg)	Treatment Frequency/Weeks	# of Patients
1	Intramuscular Arm	0.53	100	3 administrations per subject; Weeks 1, 5, and 9	7
2	Intramuscular Thigh				7

#### **6.4 Re-Treatment Criteria**

Subjects must maintain the following in order to receive each additional dose of study medication:

• ECOG performance status	0 - 1
• white blood cell count	$\geq 3,000$
• lymphocyte number	$\geq 500$
• absolute neutrophil count	$\geq 1,000$
• platelets	$\geq 90,000$
• hemoglobin	$\geq 9$
• total bilirubin	$<1.5 \times$ upper limit of normal (ULN) ( $<3 \times$ ULN if Gilbert's disease)
• AST(SGOT)/ALT(SGPT)	$<3 \times$ ULN
• creatinine	$<1.5 \times$ ULN or estimated creatinine clearance $\geq 60$ ml/min per Modified Cockcroft-Gault Formula

In addition, subjects must not have any acute grade 3 or higher hematologic and/or non-hematological adverse event that is judged possibly, probably or definitely related to the investigational drug agent and/or administration occurring on or after the first day of vaccine administration.

#### **6.5 Dose Modifications and Delays**

Dose reduction or dose increase of TA-CIN will not be permitted. The dose in this study is fixed.

In the event that TA-CIN re-treatment criteria are not met, treatment may be delayed for up to 14 days. Future doses should be delayed accordingly such that at least 23 days is maintained between each dose of TA-CIN. The timing for the Month 6, 12, and 24 assessments should be scheduled from the initial dose of TA-CIN.

#### **6.6 Unacceptable Toxicity and Early Stopping Rules**

Unacceptable toxicities are defined as treatment-related  $\geq$  grade 4 AEs, or treatment-related grade 3 AEs not improving to  $\leq$  grade 2 under therapy within 2 weeks. Exceptions include: Grade 3 lymphopenia. Because this is a pilot study evaluating safety of immunization, the stopping rule for safety is the presence of vaccine attributable (either probably or definitely) systemic grade 3 or 4 toxicities or grade 4 local/skin toxicities in  $\geq 20\%$  of patients in the study. Patients will be withdrawn from study if they manifest Grade 3 or 4 systemic toxicity attributable to vaccination with TA-CIN or grade 4 local/skin toxicities attributable to vaccination with TA-CIN. In the event of two identical unexpected treatment-related Grade 4 toxicities, accrual will be suspended pending further review.

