### 7.1.2 Serious Adverse Event (SAE)

A serious adverse event is an undesirable sign, symptom or medical condition which:

- Results in death
- Is life threatening (defined as an event in which the subject was at risk of death at the time of the event; it does not refer to an event which hypothetically might have caused death if it were more severe)
- Requires inpatient hospitalization or causes prolongation of existing hospitalization (see note below for exceptions) for  $\geq 24$  hours
- Results in persistent or significant disability/incapacity
- Is a congenital anomaly/birth defect (note: reports of congenital anomalies/birth defects must also be reported on the Pregnancy Supplemental Form)
- Is an important medical event (defined as a medical event(s) that may not be immediately life-threatening or result in death or hospitalization but, based upon appropriate medical and scientific judgment, may jeopardize the subject or may require intervention [e.g., medical, surgical] to prevent one of the other serious outcomes listed in the definition above.). Examples of such events include, but are not limited to, intensive treatment in an emergency room or at home for allergic bronchospasm; blood dyscrasias or convulsions that do not result in hospitalization.)

Events **not** considered to be serious adverse events are hospitalizations for the:

- Admissions as per protocol for a planned medical/surgical procedure
- Routine health assessment requiring admission for baseline/trending of health status (e.g., routine colonoscopy)
- Medical/surgical admission for purpose other than remedying ill health state and was planned prior to entry into the study. Appropriate documentation is required in these cases
- Admission encountered for another life circumstance that carries no bearing on health status and requires no medical/surgical intervention (e.g., lack of housing, economic inadequacy, care-giver respite, family circumstances, administrative).

The definition of serious adverse event (experience) also includes *important medical event*. Medical and scientific judgment should be exercised in deciding whether expedited reporting is appropriate in other situations, such as important medical events that may not be immediately life-threatening or result in death or hospitalization but may jeopardize the patient or may require intervention to prevent one of the other outcomes listed in the definition above. These should also usually be considered serious.

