- Approximately one week prior to each MEC meeting, the study team will submit the following items to MEC personnel for review and discussion at the meeting (The PI may join the MEC meeting in order to answer any questions the MEC might have):
  - A summary of the clinical trial's progress to date;
  - The latest IRB-approved consent document; and,
  - A summary of all adverse events, serious adverse events, deaths, and withdrawals to date.

Note that the MEC reserves the right to halt trial accrual or all study activity if, after review, serious safety concerns warrant this action. If the MEC halts study accrual or all study activity, then the study team must notify the JHU SKCCC SMC, JHU IRB, and the FDA immediately.

[name] will be holding the IND for this study. He will comply with all regulated reporting requirements to the FDA.

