### 12.4 Early Stopping Rules

This study will evaluate two different sites of TA-CIN vaccine to determine the safety

and effectiveness of TA-CIN in patients with a history of advanced cervical cancer. For each injection site, the SAE rate of 20% or more is deemed unsafe. A total of 15 patients will be enrolled, with 7-8 patients in each injection site cohort.

The study will be stopped early if there are more than two patients with SAEs observed during the study. If the SAE rate is 20% or more, there is at least 55% chance to stop the study early with 15 patients.

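### The 20% stopping rule in Section 6.6 does not name grade 5, so read literally a vaccine-attributable death may not count; Section 12.4 closes most of that gap but not all of it

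*Combined protocol and SAP*

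**What the plan says.** Section 6.6 contains three provisions that matter here.

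- It opens with "Unacceptable toxicities are defined as treatment-related" events of grade 4 or above, plus grade 3 events that do not improve within two weeks. This definition has no upper limit.
- The study stopping rule then counts patients with probably or definitely attributable "systemic grade 3 or 4 toxicities or grade 4 local/skin toxicities", with a threshold of 20% of the patients in the study. This list stops at grade 4.
- A separate provision reads "In the event of two identical unexpected treatment-related Grade 4 toxicities, accrual will be suspended pending further review". It also names grade 4 only.

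Elsewhere the grading is open at the top. Section 6.4 says that, to be re-dosed, "subjects must not have any acute grade 3 or higher hematologic and/or non-hematological adverse event" judged at least possibly related. Section 7 adopts CTCAE version 4.0, and the SAE form in Appendix D gives death its own box as grade 5.

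Section 12.4 sets a second formal rule: "The study will be stopped early if there are more than two patients with SAEs observed during the study". Section 7.1.2 lists "Results in death" among the criteria for an SAE, with no test of cause. Deaths therefore count under 12.4 whether or not they are related to the vaccine.

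**The concern.** A toxicity stopping rule should count the worst outcome at least as readily as the lesser ones. As worded, 6.6 counts an attributable systemic grade 3 event but not an attributable death, unless that patient also has a grade 3 or 4 event on record. The open-ended wording in the first sentence of the same section and in 6.4 suggests a drafting slip rather than a choice.

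Safety is the primary objective in Section 2.1. Section 8.1 says that no patient with a history of advanced cervical cancer had yet received the vaccine, and Section 6.1 names anaphylaxis as a possible risk. A rapidly fatal reaction might be recorded only as grade 5. A pre-specified rule should not leave its treatment to interpretation at that moment.

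**Working it through.** **Inputs.** Total 15 patients (12.4). The 6.6 threshold is 20% of patients, attributable events, grades as listed. The 12.4 threshold is more than two, so at least three, patients with SAEs of any cause.

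**The plan's own figure for 12.4.** It states at least a 55% chance of stopping if the SAE rate is 20%. With X binomial:

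- n = 15: P(X ≥ 3) = 1 − (0.0352 + 0.1319 + 0.2309) = 0.602
- n = 14: P(X ≥ 3) = 0.552

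The statement is true as a lower bound at 15 patients. The figure of 55% itself matches 14. Nothing below depends on it.

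**Set-up.** Let d be the patients with an attributable death and no recorded grade 3 or 4 event, g those with a non-serious attributable systemic grade 3 event, and s those with a serious attributable systemic grade 3 or 4 event.

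- 6.6 as written: (g + s)/N ≥ 20%
- 6.6 with grade 5 included: (d + g + s)/N ≥ 20%
- 12.4: d + s ≥ 3

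**Denominator 15.** Since 20% of 15 is 3, the 6.6 rule needs three patients.

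- Example: d = 1, g = 2, s = 0. As written, 2/15 = 13.3%, not met. Under 12.4, one SAE patient, not met. With the death counted, 3/15 = 20.0%, met.
- Contrast: d = 1, g = 0, s = 2. As written, 13.3%, not met, but 12.4 has three SAE patients and stops the study. There is no gap.

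**All combinations at 15.** The wording changes the 6.6 result when g + s ≤ 2 and d + g + s ≥ 3:

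| g + s | Splits of g and s | Possible values of d | Combinations |
|---|---|---|---|
| 0 | 1 | 3 to 15 (13 values) | 13 |
| 1 | 2 | 2 to 14 (13 values) | 26 |
| 2 | 3 | 1 to 13 (13 values) | 39 |

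The total is 78. Section 12.4 catches those with d + s ≥ 3, which is 74. The four that escape both rules, as (d, g, s), are (1, 2, 0), (1, 1, 1), (2, 1, 0) and (2, 2, 0). Each includes at least one non-serious grade 3 patient. With 14 patients (two groups of 7), 20% is 2.8, so three are still needed; 12.4 catches 68 of 72 and the same four escape. These counts are unweighted and are not probabilities.

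**Denominator of patients enrolled so far.** Section 6.6 does not say which denominator applies, so this reading is an assumption.

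| Enrolled | Patients needed for 20% | Missed by both rules |
|---|---|---|
| 1 to 5 | 1 | one or two deaths alone |
| 6 to 10 | 2 | one death plus one other qualifying patient, serious or not; two deaths alone; two deaths plus one non-serious grade 3 |
| 11 to 15 | 3 | the four combinations above |

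- At n = 5, one attributable non-serious grade 3 event is 1/5 = 20.0% and stops the study; one attributable death counts as 0/5 and does not.
- One qualifying patient plus one death: 1/6 = 16.7% as written against 2/6 = 33.3% with the death, falling to 1/10 = 10.0% against 2/10 = 20.0%. At most two patients have SAEs.
- Two qualifying patients plus one death: 2/10 = 20.0% already meets the rule without the death. From patient 11 it does not: 2/11 = 18.2% against 3/11 = 27.3%.

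**Suspension sentence.** No denominator is involved. Two identical unexpected treatment-related deaths with no recorded grade 4 event do not meet it literally, and they make only two SAE patients under 12.4.

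**The case against.** The strongest reply is that 6.6 asks only whether attributable grade 3 or 4 toxicity was present. A fatal reaction would usually pass through that severity, and Sections 7 and 7.5.1 require all adverse events to be recorded, so most such patients would count. That is right, and it limits the gap to deaths with no recorded grade 3 or 4 event. It does not remove it, because the plan does not say that a lower grade must be recorded separately when the outcome is fatal.

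The second reply is that deaths are well covered elsewhere. SAEs reach the sponsor within 24 hours, safety meetings are weekly, the DSMB reviews every six months, and the medical expert committee receives "A summary of all adverse events, serious adverse events, deaths, and withdrawals to date" and may halt the study. An attributable death would almost certainly prompt immediate review. This stands as a reason to rate the point low. But halting by those routes is discretionary, and a formal rule exists so that stopping does not rest on judgement alone.

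Third, the edit would not make a single death stop the study at full enrolment: 1/15 = 6.7%. That is true. A pause after any attributable death would be a different rule. The edit only makes the existing rules count what they should already count.

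Finally, an asymptomatic grade 4 laboratory value might be non-serious too, although the SAE form labels grade 4 as life-threatening. If so, the gap is slightly wider than shown.

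**Conclusion.** The concern holds as a minor wording defect. Taken literally, the 20% rule and the suspension sentence in 6.6 leave out grade 5, contrary to the open-ended grading used in the same section and in 6.4. Section 12.4 covers most of the consequences. With 15 as the denominator, what remains is one or two attributable deaths combined with one or two non-serious grade 3 patients: 4 of 78 combinations. If the 20% runs on patients enrolled so far, the gap also includes one or two deaths alone among the first ten patients, depending on the number enrolled.

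This rests on three assumptions: the fatal event has no separately recorded grade 3 or 4 toxicity, the events are probably or definitely attributable, and grade 4 events are serious. No estimate, analysis or sample-size figure is affected.

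**What to change.** In Section 6.6, reword the stopping rule to count *systemic toxicities of grade 3 or higher, or local/skin toxicities of grade 4 or higher*, and reword the suspension sentence to refer to *Grade 4 or higher*. The patient-level withdrawal sentence also stops at grade 4, but that has no consequence for a death.

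The cost is a few words in two sentences. The 20% threshold, Section 12.4, the sample size and data collection stay as they are. The edit does not settle which denominator the 20% refers to; that is a separate clarification.
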